### 7.1.2. Definition of Adverse Events

An AE is any untoward medical occurrence in a patient or clinical investigation subject, temporally associated with the use of a medicinal product, whether or not considered related to the medicinal product.

NOTE: An AE can therefore be any unfavorable and unintended sign (including an abnormal laboratory finding), symptom, or disease (new or exacerbated) temporally associated with the use of a medicinal product.

Events meeting the definition of an AE **include**:

- Any abnormal laboratory test results (hematology, clinical chemistry, or urinalysis) or other safety assessments (e.g., ECGs, radiological scans, vital signs measurements), including those that worsen from baseline, and felt to be clinically significant in the medical and scientific judgement of the investigator.
- Exacerbation of a chronic or intermittent pre-existing condition including either an increase in frequency and/or intensity of the condition.
- New conditions detected or diagnosed after study treatment administration even though it may have been present prior to the start of the study.
- Signs, symptoms, or the clinical sequelae of a suspected interaction.
- Signs, symptoms, or the clinical sequelae of a suspected overdose of either study treatment or a concomitant medication (overdose per se will not be reported as an AE/SAE unless this is an intentional overdose taken with possible suicidal/self-harming intent. This should be reported regardless of sequelae.).

Events that **do not** meet the definition of an AE include:

- Any clinically significant abnormal laboratory findings or other abnormal safety assessments that is associated with the underlying disease, unless judged by the investigator to be more severe than expected for the subject's condition.
- The disease/disorder being studied or expected progression, signs, or symptoms of the disease/disorder being studied, unless more severe than expected for the subject's condition.
- Medical or surgical procedure (e.g., endoscopy, appendectomy); the condition that leads to the procedure are an AE.
- Situations where an untoward medical occurrence did not occur (social and/or convenience admission to a hospital).

- Anticipated day-to-day fluctuations of pre-existing disease(s) or condition(s) present or detected at the start of the study that do not worsen.

### 7.1.3. Definition of Serious Adverse Events

If an event is not an AE per Section 7.1.2, then it cannot be an SAE even if serious conditions are met (e.g., hospitalization for signs/symptoms of the disease under study, death due to progression of disease, etc).

An SAE is any untoward medical occurrence that, at any dose:

- a. Results in death
- b. Is life-threatening

NOTE: The term ‘life-threatening’ in the definition of ‘serious’ refers to an event in which the subject was at risk of death at the time of the event. It does not refer to an event, which hypothetically might have caused death, if it were more severe.

- c. Requires hospitalization or prolongation of existing hospitalization

NOTE: In general, hospitalization signifies that the subject has been detained (usually involving at least an overnight stay) at the hospital or emergency ward for observation and/or treatment that would not have been appropriate in the physician’s office or out-patient setting. Complications that occur during hospitalization are AEs. If a complication prolongs hospitalization or fulfills any other serious criteria, the event is serious. When in doubt as to whether “hospitalization” occurred or was necessary, the AE should be considered serious.

Hospitalization for elective treatment of a pre-existing condition that did not worsen from baseline is not considered an AE.

- d. Results in disability/incapacity, or

NOTE: The term disability means a substantial disruption of a person’s ability to conduct normal life functions. This definition is not intended to include experiences of relatively minor medical significance such as uncomplicated headache, nausea, vomiting, diarrhea, influenza, and accidental trauma (e.g. sprained ankle) which may interfere or prevent everyday life functions but do not constitute a substantial disruption.

- e. Is a congenital anomaly/birth defect
- f. Medical or scientific judgment should be exercised in deciding whether reporting is appropriate in other situations, such as important medical events that may not be immediately life-threatening or result in death or hospitalization but may jeopardize the subject or may require medical or surgical intervention to prevent one of the other outcomes listed in the above definition. These should also be considered serious. Examples of such events are invasive or malignant cancers, intensive treatment in an emergency room or at home for allergic bronchospasm, blood dyscrasias or convulsions that do not result in hospitalization, or development of drug dependency or drug abuse.

g. Is associated with liver injury **and** impaired liver function defined as:

- ALT  $\geq 3$ xULN and total bilirubin\*  $\geq 2$ xULN ( $>35\%$  direct), **or**
- ALT  $\geq 3$ xULN and INR\*\*  $>1.5$ .

\* Serum bilirubin fractionation should be performed if testing is available; if unavailable, measure urinary bilirubin via dipstick. If fractionation is unavailable and ALT  $\geq 3$ xULN and total bilirubin  $\geq 2$ xULN, then the event is still to be reported as an SAE.

\*\* INR testing not required per protocol and the threshold value does not apply to subjects receiving anticoagulants. If INR measurement is obtained, the value is to be recorded on the SAE form.

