### **3.4. Benefit-Risk Assessment**

Belimumab administered by IV infusion is indicated for reducing disease activity in adult patients with active autoantibody positive SLE who are receiving standard therapy. The benefit/risk profile of belimumab for systemic lupus erythematosus remains favorable. Identified risks include hypersensitivity/infusion reactions and non-opportunistic infections. Potential risks (i.e., based on pharmacology but no association identified to date) include progressive multifocal leukoencephalopathy (PML) and other opportunistic infections; malignancies; immunogenicity; effects on immunizations (including interactions with live vaccine); and psychiatric events including depression and suicidality. The most common AEs reported in the primary safety population of adults with SLE were associated with hypersensitivity/infusion-related reactions, non-opportunistic infections, and symptoms consistent with SLE. The majority of reports of infusion-related and hypersensitivity reactions were non-serious and include symptoms such as nausea, vomiting, diarrhea, chills, fever, rash, urticaria, pruritus, headache, dizziness, and dyspnoea. However, infusion and hypersensitivity reactions can be severe and fatal. Most clinical trial and spontaneous cases of serious hypersensitivity occurred during or within the first hour after the completion of the infusion, although some cases report delayed acute onset (>4 hours but <4 days) or a delayed non-acute onset (4-21 days) hypersensitivity reactions.

Infections have been reported with administration of belimumab and are also associated with both SLE and immunosuppressant medication used to treat SLE. The mechanism of action of belimumab may increase the potential risk for the development of infections. In the phase 2 and 3 clinical trials, there was a slight increase in the overall rate of infections in the belimumab group compared with the placebo group. There was no difference in the rate of serious infections, infections leading to discontinuation, or infections of special interest. Out to 10 years in the Phase 2 and 3 continuation studies, the incidence rate of serious infections has remained stable or declined over time. No association between

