#### **7.1.4. Laboratory and Other Safety Assessment Abnormalities Reported as AEs and SAEs**

Any abnormal laboratory test results (haematology, clinical chemistry, or urinalysis) or other safety assessments (e.g., ECGs, radiological scans, vital signs measurements), including those that worsen from baseline, and felt to be clinically significant in the medical and scientific judgement of the investigator are to be recorded as AEs or SAEs.

However, any clinically significant safety assessments that are associated with the underlying disease, unless judged by the investigator to be more severe than expected for the subject's condition, are not to be reported as AEs or SAEs.

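### SLE worsening judged to be within expectation is kept out of AEs and SAEs, even with hospitalisation or death, and the plan records it elsewhere only indirectly

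*Protocol*

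**What the plan says.** Protocol Section 7.1.2 has two lists. The first, of events that are AEs, includes "Exacerbation of a chronic or intermittent pre-existing condition including either an increase in frequency and/or intensity of the condition". The second, of events that are not AEs, includes the disease studied and its "expected progression, signs, or symptoms of the disease/disorder being studied, unless more severe than expected for the" subject's condition.

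Section 7.1.3 opens with a threshold rule: an event that fails the AE definition in Section 7.1.2 "cannot be an SAE even if serious conditions are met (e.g., hospitalization for signs/symptoms of the disease under study, death due to progression of disease". The severity qualifier is not repeated in these examples. The seriousness criteria, starting with death, come after this rule.

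Section 7.1.4 takes out of AE and SAE reporting "any clinically significant safety assessments that are associated with the underlying disease, unless judged by the investigator to be more severe than expected" for that subject. No section defines what severity is expected, defines a flare, or provides for adjudication.

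The safety endpoints (Protocol Section 2; SAP Section 3.2) are adverse events, vital signs, ECG and laboratory tests. Safety is a secondary objective; the primary objective is pharmacokinetic.

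**The concern.** Every subject has SLE, so a flare is a foreseeable event in the 84 days after the dose. The protocol gives an investigator one reason to record it as an AE and another not to. If the second is followed, the event leaves the SAE system as well, whatever its outcome.

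The choice depends on what was expected for that subject. It is made open label, with no scheduled measure of disease activity behind it and no control arm to show the background rate. Two sites could classify the same flare differently and both be following the text.

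A drug effect could also be absorbed into the disease. Rash, for example, appears both among the delayed hypersensitivity symptoms in Protocol Table 1 and among the SLE criteria in Appendix 2. At stake are the completeness of the AE and SAE summaries and the 24-hour notice to the sponsor of a lupus admission or death.

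**Working it through.** The plan states no figure on this point, so there is none to reproduce. The check is mainly of text.

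**1. Four events put through Sections 7.1.2 and 7.1.3**

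| Event after dosing | By the exacerbation bullet | By the disease-under-study bullet | SAE? |
|---|---|---|---|
| Flare judged worse than expected | AE | AE (qualifier applies) | Yes, if serious |
| Flare judged within expectation, no admission | AE | Not an AE | Not serious |
| Flare judged within expectation, with admission | AE | Not an AE | Barred on the second reading |
| Death put down to expected progression | AE | Not an AE | Barred on the second reading |

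Only the first row gives one answer. The examples in Section 7.1.3 are the events in the last two rows, so a site is likely to follow the second reading there.

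**2. Is there a measured reference for what was expected?**

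- Protocol Table 2 and the endpoints contain no SLEDAI, BILAG, PGA or flare index, before or after the dose. These instruments appear only in background text.
- Anti-dsDNA and ANA are listed for screening only (Table 2, footnote 8).
- Table 2 places the spot urine protein ratio at screening only, although Section 6.2.2 lists it with the repeated laboratory tests.
- Sections 5.2 and 5.3 describe a single open-label treatment.

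So there is no scheduled reference.

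**3. Where would a non-AE flare, admission or death be seen?**

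- SAP Tables 2.01 to 2.06 and Listings 11 to 18 hold AEs only, so it would not be there.
- The SAP has no separate death display. Fatal outcomes are shown within Listing 17, which covers serious AEs. A death classed as progression would not be in it.
- The 24-hour clock in Protocol Sections 7.1.1 and 7.1.10 and Table 4 applies to SAEs, so it would not start, apart from the separate liver rules.
- Laboratory change would show in SAP Tables 2.14 to 2.21, Listings 19 to 22 and the out-of-range listing (Protocol Section 9.3.4.1.3).
- A change of SLE medication, permitted after dosing (Protocol Section 5.7.1), would be in Listing 8. A withdrawal would be in Listing 2.
- Any post-mortem findings go to the sponsor (Protocol Section 7.1.11).

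None of these sources identifies the event as SLE worsening by design. A clinical flare without laboratory change would show only through a medication change or a withdrawal.

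**4. Size of one missed event**

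The denominator is the safety population, which is everyone dosed (Protocol Section 9.3.1). About 20 subjects are to be enrolled (Section 4.1).

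- If 20 are dosed: 1/20 = 5.0 percentage points.
- If only 12 are dosed: 1/12 = 8.3 percentage points. Twelve is the minimum to complete dosing and critical assessments, not the planned safety denominator.

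**The case against.** The strongest reply is that the exclusion is conditional. Worse-than-expected events return as AEs. Subjects enter on no SLE medication or a regimen stable for at least 2 months. Active CNS lupus needing intervention and severe lupus kidney disease within 6 months of screening are excluded. Against that background an SLE admission or death could readily be judged worse than expected. Other wording also leans towards reporting: Section 7.1.2 exempts day-to-day fluctuation only where there is no worsening, and Section 7.1.3 exempts elective admission only where the condition has not worsened from baseline. All of this stands. It makes the defect a conflict between rules rather than a blanket exclusion, but it does not settle the last two rows of the table above.

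A reader might infer more than the documents support:

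- *That SLE worsening would go wholly unreported.* The indirect sources listed above rule this out.
- *That listing death as a seriousness criterion contradicts the exclusion.* It does not, because the AE test comes first.
- *That PML or psychiatric events would be hidden.* Suspected PML must be reported immediately to the Medical Monitor (Section 7.3), new conditions found after dosing are AEs (Section 7.1.2), and subjects are asked to report depression and suicidality (Table 1).
- *That the AE profile cannot be compared with earlier trials.* Section 3.4 says their most common AEs were associated with hypersensitivity or infusion reactions, "non-opportunistic infections, and symptoms consistent with SLE". The documents do not give those trials' AE definitions, which may have carried the same qualifier.

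It can also be said that recording worsening still rests on unblinded judgement. That is true, but the investigator would then judge only whether the subject got worse, and no longer also whether the worsening was expected.

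**Conclusion.** The concern holds in limited form. SLE worsening judged to be within expectation is excluded from AEs and so barred from being an SAE, including where it leads to hospitalisation or death. This conflicts with the exacerbation bullet. Expected severity is undefined and no disease-activity or flare assessment is scheduled, so the AE and SAE summaries and 24-hour reporting may miss such events.

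The size is 5 percentage points per missed subject, assuming 20 are dosed. That is simply one over the denominator. The documents give no expected rate of SLE flare, admission or death, so the number likely to be missed cannot be estimated. The pharmacokinetic primary objective is not affected. The point merits correction because safety is a stated objective, the group is small and the change is cheap.

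**What to change.** - Reconcile Protocol Sections 7.1.2, 7.1.3 and 7.1.4 so that SLE worsening from baseline after dosing is recorded as an AE, expected or not.
- State that every death and every unplanned hospitalisation, including those attributed to SLE, is reported as an SAE. The planned Day 0 stay and the existing exemptions for elective and social admissions need not change.
- Add an SLE-related flag to the AE and SAE pages of the CRF.
- In the SAP, carry the flag into the AE and SAE listings so that results can be read with and without SLE-related events. Splitting Tables 2.01 and 2.05 by the flag is optional; with about 20 subjects, repeating all six AE tables is unnecessary.

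The cost is protocol wording, one CRF field, a few more AE and SAE forms, and a higher AE count that the flag explains. No visit or test is added. Disease activity would still not be measured on a scale, so the record would still depend on the investigator noticing the worsening.

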#### **7.1.4. Laboratory and Other Safety Assessment Abnormalities Reported as AEs and SAEs**

Any abnormal laboratory test results (haematology, clinical chemistry, or urinalysis) or other safety assessments (e.g., ECGs, radiological scans, vital signs measurements), including those that worsen from baseline, and felt to be clinically significant in the medical and scientific judgement of the investigator are to be recorded as AEs or SAEs.

However, any clinically significant safety assessments that are associated with the underlying disease, unless judged by the investigator to be more severe than expected for the subject's condition, are not to be reported as AEs or SAEs.

#### **7.1.5. Method of Detecting AEs and SAEs**

The investigator (or sub-investigators) will do the medical examination following the schedule with nondirective interview such as the following sentences.

- "How are you feeling?"
- "Have you had any (other) medical problems since your last visit/contact?"
- "Have you taken any new medicines, other than those provided in this study, since your last visit/contact?"

#### **7.1.6. Recording of AEs and SAEs**

When an AE/SAE occurs, it is the responsibility of the investigator to review all documentation (e.g., hospital progress notes, laboratory, and diagnostics reports) relative to the event. The investigator will then record all relevant information regarding an AE/SAE on the CRF. It is not acceptable for the investigator to send photocopies of the subject's medical records to GSK in lieu of completion of the appropriate AE/SAE CRF pages. However, there may be instances when copies of medical records for certain cases are requested by GSK. In this instance, all subject identifiers will be blinded on the copies of the medical records prior to submission to GSK.

The investigator will attempt to establish a diagnosis of the event based on signs, symptoms, and/or other clinical information. In such cases, the diagnosis should be documented as the AE/SAE and not the individual signs/symptoms.

### 7.1.7. Evaluating AEs and SAEs

The definition of an AE and a SAE is provided in Section 7.1.2 and Section 7.1.3.

### 7.1.8. Assessment of Intensity

The investigator will make an assessment of intensity for each AE and SAE reported during the study. The assessment will be based on Division of Microbiology and Infectious Diseases (DMID) Adverse Event Severity Grade Tables (see [Appendix 3](#)), where possible:

#### SEVERITY:

Mild – An event that is easily tolerated by the subject, causing minimal discomfort and not interfering with everyday activities (Grade 1 DMID)

Moderate – An event that is sufficiently discomforting to interfere with normal everyday activities (Grade 2 DMID)

Severe – An event that prevents normal everyday activities (Grade 3 or 4 DMID)

An AE that is assessed as severe is not to be confused with an SAE. Severity is a category utilized for rating the intensity of an event; and both AEs and SAEs can be assessed as severe. An event is defined as ‘serious’ when it meets at least one of the pre-defined outcomes as described in the definition of an SAE.

### 7.1.9. Assessment of Causality

The investigator (or sub-investigator) is obligated to assess the relationship between IP and the occurrence of each AE/SAE. A “reasonable possibility” is meant to convey that there are facts/evidence or arguments to suggest a causal relationship, rather than a relationship cannot be ruled out. The investigator (or sub-investigator) will use clinical judgement to determine the relationship. Alternative causes, such as natural history of the underlying diseases, concomitant therapy, other risk factors, and the temporal relationship of the event to the IP will be considered and investigated. The investigator (or sub-investigator) will also consult the IB and/or Product Information, in the determination of his/her assessment. For each AE/SAE, the investigator must document in the medical notes that he/she has reviewed the AE/SAE and has provided an assessment of causality.

There may be situations when an SAE has occurred and the investigator (or sub-investigator) has minimal information to include in the initial report to GSK. However, it **is very important that the investigator (or sub-investigator) always make an assessment of causality for every event prior to the initial transmission of the SAE**

**data to GSK.** The investigator (or sub-investigator) may change his/her opinion of causality in light of follow-up information, amending the SAE data collection tool accordingly. The causality assessment is one of the criteria used when determining regulatory reporting requirements.

The investigator (or sub-investigator) will provide the assessment of causality as per the instructions for completion of the AE/SAE data collection tool.

#### **7.1.10. Completion and Transmission of SAEs Report**

Once an investigator (or sub-investigator) becomes aware that an SAE has occurred in a study subject, she/he will report the information to GSK within 24 hours or as outlined in the protocol in the section titled, “Prompt Reporting of Serious Adverse Events and Other Events to GSK”. The SAE data collection tool will always be completed as thoroughly as possible with all available details of the event, and submitted to GSK within the designated time frames. If the investigator (or sub-investigator) does not have all information regarding an SAE, he/she will not wait to receive additional information before notifying GSK of the event and completing the appropriate data collection tool. The appropriate data collection tool will be updated when additional information is received.

The investigator (or sub-investigator) will always provide an assessment of causality at the time of the initial report as described in the section of this document titled, “Assessment of Causality”.

The primary mechanism for reporting SAEs to GSK will be the electronic data collection (EDC) tool (e.g., InForm system). If the electronic system is unavailable for greater than 24 hours, the site will use the paper SAE data collection tool and fax it to GSK. The site will then enter the serious adverse event data into the electronic system as soon as it becomes available.

GSK will provide a separate list of contact details for reporting SAEs, including fax numbers and telephone numbers.

#### **7.1.11. Follow-Up of AEs and SAEs**

After the initial AE/SAE report, the investigator (or sub-investigator) is required to proactively follow each subject and provide further information to GSK on the subject’s condition. All AEs and SAEs documented at a previous visit/contact and that are designated as ongoing, will be reviewed at subsequent visits/contacts.

All AEs and SAEs will be followed until resolution, until the condition stabilizes, until the event is otherwise explained, or until the subject is lost to follow-up. This applies to all subjects, including those withdrawn prematurely. The investigator (or sub-investigator) will ensure that follow-up includes any supplemental investigations as may be indicated to elucidate the nature and/or causality of the AE or SAE. This may include additional laboratory tests or investigations, histopathological examinations, or consultation with other health care professionals.

GSK may request that the investigator perform or arrange for the conduct of supplemental measurements and/or evaluations to elucidate as fully as possible the nature and/or causality of the AE or SAE. The investigator (or sub-investigator) is obligated to assist. If a subject dies during participation in the study or during a recognized follow-up period, the investigator will provide GSK with a copy of any post-mortem findings, including histopathology (may not be required for studies where death is an endpoint).

New or updated information will be recorded in the originally completed SAE data collection tool. The investigator (or sub-investigator) will submit the updated SAE data to GSK within the designated reporting time frames.

